During enrollment, participants have the option to consent to receiving reminders in the form of phone calls, text messages, or email over the course of the intervention, depending on personal preference. Between-session contact will be used with the goal of increasing treatment adherence and engagement. Participants may opt-out of the text message contact option at any point.

After enrollment, participants will be assigned to one of the two intervention groups using a randomized block design to ensure that equal numbers of patients are split into the p3RP-DMD and p3RP groups. To prevent participant unblinding, participants will be asked not to share specific information discussed in the group (e.g., skills learned, topics discussed) on social media sites (e.g., Facebook groups or internet chat groups) or with other acquaintances for the duration of the study. The groups will be conducted in person at MGH by trained study therapists over 12 weeks and include 10 active intervention sessions. Each session will last approximately 90 minutes. Participants will also be asked to answer follow-up assessment questionnaires 3 months following program completion. These questionnaires will be administered over the phone for 30-45 minutes.

Participants will complete demographics assessments at baseline, in addition to psychological/behavioral assessments and a 6-minute walk test at both baseline and post-test timepoints. Participants in the p3RP-DMD group will pair their Fitbit DMD to a smartphone with Bluetooth, and the Fitbit will inform an individualized quota-based behavioral plan to improve both adherence and efficacy. All participants will also wear an accelerometer for 7 days before the first treatment session (baseline) and for 7 days after the final treatment session (post-test). After each assessment week, participants will return the accelerometers in addition to a wear time log.

The following measures will be administered at all timepoints unless otherwise stated. Questionnaires at 3-month follow-up will be administered over the phone.

Demographics – *baseline only*

Credibility and Expectancy Questionnaire (CEQ) – *baseline only*

Pittsburgh Sleep Quality Index (PSQI)

PROMIS Physical Function SF

Physical Activity Scale for Individuals with Physical Disabilities (PASIPD)

WHO Disability Assessment Scale (WHODAS) 2.0

Numerical Rating Scale for Pain (NRS)

Pain Resilience Scale (PRS)

PROMIS Anxiety SF

PROMIS Depression SF

PROMIS Social Isolation SF

PROMIS Emotional Support SF

Measure of Current Status (MOCS)

Pain Catastrophizing Scale (PCS)

Tampa Kinesiophobia Scale

Cognitive and Affective Mindfulness Scale (CAMS-R)

Patient Global Impression of Change (PGIC) – *post-test and 3-month follow-up only*

Client Satisfaction Questionnaire (CSQ-3) – *post-test and 3-month follow-up only*

Participants will be given the option to complete a maximum of two make-up sessions via the Vidyo teleconferencing software. Vidyo is a HIPAA approved, secure web platform used in clinical care for patients at MGH. Participants will have a Vidyo meeting with study staff to ensure that they are comfortable using Vidyo for make-up sessions only. Ratings of patient satisfaction are high, and there have been no complaints of technological difficulties. Participants will be compensated \$20 for each of three assessments completed and \$10 for transportation (for each group session attended). They can also receive up to two additional \$25 payments for completing 6 group sessions and 8 group sessions. The maximum compensation per participant is \$230.

At study enrollment completion (e.g., no longer recruiting or enrolling, and only completing follow-up measures and data analysis), we will conduct 12 qualitative exit interviews with participants who have completed all study measures (e.g., completing questionnaires at both baseline and post-test and wearing the accelerometer at both baseline and post-test). Participants will be randomly selected to complete the interview, which will last 15 minutes and will be completed over the phone with the study clinician. We will conduct qualitative exit interviews within the following four categories: 1) 3 participants who were sedentary at baseline (i.e., less than 5,000 steps) and increased their step-count at post-test; 2) 3 participants who were sedentary and did not increase their step-count at post-test; 3) 3 participants who were not sedentary at baseline and did increase their step-count; 4) 3 participants who were not sedentary at baseline and did not increase their step-count at post-test. Participants will be called and will be contacted until clinician is able to speak to participant. If a participant declines, a new random participant number will be selected.

VI. BIOSTATISTIC ANALYSIS

Phase I

The qualitative focus group data and individual exit interview data will be transcribed and analyzed, using NVivo 10 qualitative software, and we will conduct thematic content analysis using guidelines provided by Miles and Huberman (1984). The 2 coders ([name] and study clinician) will meet on an ongoing basis with [name] to discuss the structural thematic framework, categories, and coding plan. To ensure coding reliability, coding discrepancies will be resolved through discussion and comparison of raw data. Coding will continue until a high reliability (Kappa= >0.80) is established. Once these data analyses are completed, the multidisciplinary team will provide the expert review of data, to discuss the interpretation of our findings in the context of current research on chronic heterogeneous pain.

Phases II and III

The p3RP-DMD intervention group will use a Fitbit DMD through which participants will use Fitbit accounts with deidentified physical measurements (i.e., height and weight) and profile information with approximate birthdays (e.g., month and year only). Participant account names will be set up with a study ID number as the first name and “Participant” as the last name. De-identified DMD data will be processed securely through the Fitbit data collection company, Fitabase. Fitabase does not store identifiable data and all participant data is uploaded through encrypted server communication and stored in a highly secure infrastructure.

The qualitative exit interview data will be transcribed and analyzed, using NVivo 10 qualitative software, and we will conduct thematic content analysis using guidelines provided by Miles and Huberman (1984). The 2 coders ([name] and study clinician) will meet on an ongoing basis to discuss the structural thematic framework, categories, and coding plan. To ensure coding reliability, coding discrepancies will be resolved through discussion and comparison of raw data. Coding will continue until a high reliability (Kappa= >0.80) is established. Once these data analyses are completed, the multidisciplinary team will provide the expert review of data, to discuss the interpretation of our findings in the context of current research on chronic heterogeneous pain.

VII. RISKS AND DISCOMFORTS

Patients will be informed that there are no foreseeable physical risks from this research study. They will be informed that in the unlikely situation that they might feel uncomfortable with the topic of discussing within the group, they can alert the group leader who will provide help, as needed.

As Vidyo is HIPAA approved and secure, there are no risks associated with its use. However, participants will be asked to ensure that they are in a private room during the group sessions, to protect their privacy and that of group members. As with any group studies, there may be confidentiality issues, but we will discuss the importance of maintaining confidentiality at the beginning of each group.

VIII. POTENTIAL BENEFITS

Patients will be informed that there may be no direct benefit from participating in this research study. Some patients may become more physically active, more resilient, better able to cope with pain and stress, and experience a better quality of life.

In the future, knowledge from this research may benefit others by providing information on how to better mind body interventions for patients with chronic pain.

IX. MONITORING AND QUALITY ASSURANCE

Phase I: The focus groups will be conducted uniformly using a semi structured interview script that will be finalized during the first few months of the study. The Principal Investigator will be responsible for ensuring compliance with IRB procedures.

Phase II: Study therapists will have weekly team meetings and clinical supervision. Study staff will follow the patient manuals for each group and assure that all items on all questionnaires have been addressed. Once completed, data will be checked for out of range values using frequency distributions prior to analyzing the data. The Principal Investigator will be responsible for ensuring compliance with IRB procedures.

Phase III: Feasibility will be assessed as depicted in the prior section. We will calculate the proportion of patients who complete at least 6 of the 8-planned treatment sessions (75%), along with the 95% confidence interval (CI) around this discontinuation rate. Treatments are considered feasible if over 70% of participants complete at least 6 treatment sessions.

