Physical function, defined following the ICF⁹, implies “a person’s capacity in a set of situations and includes engagement in meaningful aspects of one’s life including performing activities of daily living such as household chores, walking, work and self care” and is consistently associated with mental and physical health benefits³⁰. New recommendations from IMMPACT released during the summer of 2016⁸ focus primarily on physical function, and urge researchers to directly target it during pain clinical trials as well as to conceptualize it comprehensively through self report measures of activity of daily living and physical activity (biased due to perceptions but important to patients), performance based measures (e.g., walk test; still subject to bias due to motivation and perceptions), and more objective measures of physical activity such as accelerometers or other digital monitoring devices like the Fitbit (which are valid and comparable to live observations of activity). **No mind body studies in chronic pain to date have comprehensively addressed and assessed physical function/activity consistent with ICF⁹ and IMMPACT⁸ 2016 criteria.** This represents an unexplored opportunity to improve outcomes and sustain improvements in this population.

1.3. Quota based walking is associated with improved outcomes in chronic pain patients, but not incorporated within mind

body programs. The US Department of Public Health's research has shown a clear relationship between daily physical activity such as a 30-minute walk and several health related outcomes such as mortality, cardiovascular diseases and cancer⁴⁸.

Patients with chronic pain are sedentary and take significantly fewer steps per day than an average healthy adult⁴⁹⁻⁵².

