3.1 Procedures Overview

The present proposal aims to adapt, pilot and examine the credibility, acceptability, adherence and feasibility of the 3RP adapted for chronic pain (p3RP), and the p3RP-DMD, which is the pain specific 3RP integrated with a commercial digital monitoring device (DMD), the Fitbit. This R34 feasibility project will lay the groundwork for a large RCT of the p3RP-DMD vs p3RP vs pHEP attention placebo control, and will help understand whether the DMD Fitbit is

necessary to comprehensively improve function. Consistent with prior theory within a subsequent R01 we will test the hypothesis that the p3RP-DMD will be superior to the p3RP and pHEP in improving and sustaining improvements in

objective, performance based and self-reported physical and emotional function in patients with heterogeneous chronic pain. Using the specific NCCIH R34 mechanism we now follow an iterative design^{82,83} to adapt the general 3RP and refine both the p3RP and the integrated p3RP-DMD interventions to maximize feasibility, acceptability, credibility, recruitment protocol, adherence and measurements for patients with heterogeneous chronic pain. To allow objective measurement of activity in both p3RP and p3RP-DMD groups, we will use Accelerometer DMDs for 1 week at baseline and post-test. The Fitbit DMD will be used to address/reinforce activity consistent with an individualized pacing plan, and to assess daily activity during the program only for those randomized to the p3RP-DMD.

During the RCT phase, participants will be randomized 1:1 to p3RP-DMD or p3RP using block randomization. The study team will be blinded and the program manager, not involved in the study, will be responsible for assigning numbers to each participant. Participants will not know whether they are assigned to the p3RP-DMD intervention or the p3RP control. Rather, they will be informed that they will be randomized to one of 2 physical activity groups, in an effort to identify which one works best in patients with chronic pain. In order to prevent unblinding, participants will be asked to not share information discussed in the group on social media sites (e.g., Facebook groups or internet chat groups) or with other acquaintances for the duration of the study. We will also explain to study participants how sharing of information would potentially negatively impact the validity of study results.

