3.2. The 3RP. The novel 8-week group-based general 3RP¹⁰ has been developed by a team led by [name] aided by [name], and will be further adapted for patients with heterogeneous chronic pain including increased physical activity. Drs. [name] and [name] have extensive experience adapting and delivering the 3RP to a variety of populations (see preliminary data). [name] published the first and only RCT¹⁶ of the 3RP adapted for patients with neurofibromatosis (NF; 3RP-NF) and found excellent feasibility and acceptability, as well as level 2 evidence of improvement in quality of life in those randomized to 3RP-NF versus those who attended the attention placebo control HEP-NF; improvements maintained at 6 months follow-up. The 3RP model and proposed adaptations for the needs of patients with chronic pain, including integration of DMD are depicted in Figure . A description of each of the 8 general 3RP group sessions as well as adaptations for proposed for the p3RP-DMD are depicted in Table 1. Adaptations for the pain specific p3RP will be identical but will not include DMD integration adaptations. The 3RP introduces and reinforces new skills through didactics, in-session activities, discussions, and daily home practice assignments. Homework involved setting SMART goals, recording type and amount of daily RR practice, and recording daily 1-3 appreciations. Each session begins with the practice of a new exercise to elicit the RR. The relaxation method is then coordinated with the remaining session content. For instance, the clinician may introduce imagery of a peaceful place as a relaxation method, and then transition to didactics and exercises that focus on skills for building a positive perspective. The main proposed adaptation is the focus on pain as a stressor, rather than on general stress, and uses skills to directly target increased physical activity. General adaptations will include: 1) setting weekly SMART goals specific to quota based pacing to increase activity, individualized to each patient based on baseline or subsequent activity level in the previous block, and instruction on how to pair these with feedback from Fitbit (in the p3RP-DMD only); 2) modification of all RR exercises to address habituation to pain, mindfulness when experiencing pain; 3) employment of RR during exercise to cope with pain and increase enjoyment; 4) pairing exercise with activities of daily living that are important to participants, and link these within the SMART goals; 5) education information of the benefits of exercise, decrease sedentary time, and healthy patterns of activity in chronic pain through non pain contingent pacing; 6) pain specific adaptations of all skills (pain acceptance, restructuring of nonadaptive pain thoughts, etc); 7) specific Fitbit instructions (charging, downloading, using feedback, etc).

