
Inclusion Criteria	Rationale
Male and female outpatients, age 18 years or older	Population under study
Have nonmalignant chronic pain for more than 3 months	International Association for Study of Pain (IASP) ¹ criteria
Able to perform a 6-minute walk test	Program will involve increase number of steps/outcome measure
Owns a smartphone with Bluetooth 4.0	Necessary for pairing with DMD and storing/downloading data.
Willingness and ability to participate in the 3RP-DMD intervention and to comply with the requirements of the study protocol (including weekly sessions and daily DMD use).	Human Subjects concern, feasibility
Free of concurrent psychotropic or pain medication for at least 2 weeks prior to initiation of treatment, OR stable on current psychotropic or pain medication for a minimum of 6 weeks and willing to maintain a stable dose	Treatment confound
Leads a sedentary lifestyle	Treatment confound
Exclusion Criteria	Rationale
Diagnosed with a medical illness expected to worsen in the next 6 months (e.g., malignancy)	Treatment confound
Serious mental illness or instability for which hospitalization may be likely in the next 6 months	Feasibility, participant safety
Current suicidal ideation reported on self-report	Subject safety
Lifetime history of schizophrenia, bipolar disorder, or other psychotic disorder, current substance abuse or dependence and	Treatment confound
Current substance use disorder, within the past 6 months	Treatment confound
Practice of yoga/meditation, or other mind body techniques that elicit the RR, once per week for 45min or more within the last 3 months or less.	Treatment confound
Regular use of DMD in the last 3 months.	Treatment confound

Engagement in regular intensive physical exercise for >30 min daily.	Treatment confound
Unable to walk without use of assistance (e.g., walker, cane, wheelchair)	Treatment confound
Limitations/restrictions on physical activity due to health conditions	Feasibility, participant safety

Adaptations for the p3RP will follow the same framework without any of the DMD specific adaptations. All adaptations will occur after input from patients through the focus groups.

II. SPECIFIC AIMS

Specific aims for phase I are:

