Aim 1: In the first step our multidisciplinary team will propose modifications to the general 3RP to address the needs of patients with chronic pain reported in the literature, with a focus on improving physical activity and function (see Figure , Table 1). Based on this information, we will develop a semi-structured qualitative interview script.

Hypotheses: NA

Aim 2: In the second step we will use the semi-structured qualitative interview to guide focus groups (30 total) to gather feedback on the intervention components, gauge treatment needs and expectations, as well as barriers and ways to facilitate participation in the intervention and adherence to the use of DMD and 3RP specific practice, among chronic pain patients. Participants will also be given an exit interview to answer questions that they might not feel comfortable discussing during the group setting (e.g., triangulation).

Hypotheses: NA

Specific aims for phase II are:

Aim 3: In the first step, we will pilot the adapted p3RP-DMD and p3RP programs in two initial groups (N=10/group, 20 total) of chronic pain patients and assess preliminary credibility, acceptability, satisfaction of treatment, feasibility (of recruitment and instruments) and adherence to the use of the DMD and to p3RP-specific homework.

Hypotheses: N/A

Aim 4: In the second step, we will conduct a semi-structured comprehensive qualitative exit interview at the end of the groups focused on discussing patients' perception of the rationale for and helpfulness of each individual p3RP specific module, patients' perception of the rationale and helpfulness of using the DMD in increasing physical activity/function, patients' perception of the importance and ease of adherence to DMD and adherence to p3RP specific homework, and patients' burden of questionnaire completion.

Hypotheses: N/A

Specific aims for phase III are:

Aim 5: We will conduct an RCT (N = 80 chronic pain patients, 40/arm, 8 groups total, accounting for 25% attrition) of the newly refined p3RP-DMD versus the newly refined p3RP. We will compare the credibility, acceptability, adherence, satisfaction with treatment, feasibility (of recruitment, refined intervention, study procedures, and instruments) between the two interventions.

Hypotheses: N/A

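### Section 3.1 claims that the study team and participants are blinded, but this cannot hold for participants (as to the device), therapists or adherence raters, and no procedure supports it for outcome assessors or analysts

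*Combined protocol and SAP*

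**What the plan says.** Section 3.1 (Procedures Overview) makes two unqualified statements about the randomized phase. On staff: "The study team will be blinded and the program manager, not involved in the study", who assigns a number to each participant. On participants: "Participants will not know whether they are assigned to the p3RP-DMD intervention or the p3RP control". It then adds: "Rather, they will be informed that they will be randomized to one of 2 physical activity groups". Participants are also asked not to pass on what is discussed in their group. Section V, Phase III, repeats that request and gives prevention of participant unblinding as the reason.

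Other passages describe what each arm receives and who handles it:

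- Section 3.1: the Fitbit serves to reinforce a pacing plan and "to assess daily activity during the program only for those randomized to the p3RP-DMD".
- Section 3.2: the goal-setting content includes "instruction on how to pair these with feedback from Fitbit (in the p3RP-DMD only". The p3RP programme is otherwise the same, without the device material.
- Eligibility table after section 3.2: candidates must be willing and able "to comply with the requirements of the study protocol (including weekly sessions and daily DMD use".
- Section V, Phase III: p3RP-DMD participants pair the Fitbit to a smartphone, study therapists run the groups face to face, a walk test is done at baseline and post-test, and the 3-month questionnaires are given by telephone.
- Section IX: adherence to the manual is rated from audio recordings and checklists.
- Section III: investigators at MGH manage and analyze the data.

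**The concern.** A reader of section 3.1 would take the trial to be blinded for both participants and the whole study team. The two arms differ by a wearable device that only one of them gets, so anyone who wears it, teaches with it or hears it taught knows the arm.

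This matters in two ways. First, the trial would report a property that it does not have, and section 3.1 presents the project as groundwork for a larger trial. Second, the blanket sentence is the only masking offered for two outcome assessments: the post-test walk test and the 3-month calls. Under Aim 5 in section II, "We will compare the credibility, acceptability, adherence, satisfaction with treatment, feasibility" between the two interventions. Satisfaction is measured by the CSQ-3, which is among the questionnaires given by phone at 3 months.

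**Working it through.** No figure in the plan is at issue, so the check sets the blinding claim against the described procedures, role by role.

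1. **Participants.** The claim is that they do not know their arm. The Fitbit belongs to p3RP-DMD only (section 3.1), and its participants pair it to a phone (section V, Phase III). Each participant therefore knows whether they have the device. The neutral description of two activity groups can hide the hypothesis, or which arm counts as the control, but not the device. The recruitment post in section III weakens even that for those who see it, because it frames the study question as activity with a Fitbit or without one.
2. **Therapists.** The claim is that the team is blinded. Therapists lead the groups (section V), and Fitbit content exists in one arm only (section 3.2). They know the arm.
3. **Adherence raters.** They listen to recordings of those sessions (section IX). That they hear the arm-specific content is an inference, but a direct one from sections 3.2 and IX.
4. **Walk testers and phone callers.** Section V names neither by role and gives no masking step. The program manager's number assignment concerns allocation and masks nobody afterwards. The result is missing support, not impossibility.
5. **Analysts.** Section III says who they are (investigators at MGH). Neither it nor section VI gives a masking step. The result is again missing support.

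The number of assessments resting on item 4 can be counted:

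- Participants: 80 randomized (Aim 5). With the planned 25% attrition, 80 × (1 − 0.25) = 60. The range is 60 to 80 post-test walk tests and 60 to 80 calls.
- Questionnaires per call: section V lists 18 items, of which 2 (demographics and the CEQ) are baseline only, so 18 − 2 = 16. Of these, 14 are given at every timepoint and 2 (PGIC and CSQ-3) at post-test and follow-up only.
- Post-test questionnaires are left out, because their mode of administration is not stated.

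**The case against.** The strongest defence is that section 3.1 is loosely worded rather than wrong. Its follow-on sentence about two activity groups suggests that the authors meant masking to the hypothesis, and the sentence on the study team also covers number assignment by an outsider, so it may mean concealment of allocation. Both readings are possible. They show that the procedures deliver less than the text claims; they do not make the text true, and on the second reading the protocol has no assessor masking at all.

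The point about limited consequence stands. Phase III is a feasibility phase whose aims state no hypotheses. The session-completion criterion in section IX and the accelerometer data do not depend on who assesses. Credibility (CEQ) is collected at baseline only. Masking a tester or caller limits staff influence; it does not remove self-report or motivation bias in participants who know they have the device.

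Four stronger readings are tempting, and the documents do not support them:

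- A reader might infer that assessors and analysts are in fact unblinded. The documents only fail to show how they would be masked.
- A reader might infer that nobody is named for the quantitative analysis. Section III does name investigators at MGH; only the masking step is absent.
- A reader might take the remark in section 1.2 on "performance based measures (e.g., walk test; still subject to bias due to motivation and perceptions" as evidence about testers. In context it most naturally refers to the patient's own motivation and perceptions.
- A reader might infer from section VI, where Fitbit accounts carry the study ID, that testers or callers can read the arm. No passage gives them access to those accounts.

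**Conclusion.** The blinding statement in section 3.1 is wrong as written for participants as to the device, for therapists and for adherence raters. For walk testers, callers and analysts it is unsupported. It should be corrected, because it describes a property that the trial would report and the correction is cheap. It does not undermine the feasibility aims.

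No bias can be sized from the documents and none is claimed. The exposure is 60 to 80 walk tests and 60 to 80 calls of 16 questionnaires each. One of those questionnaires, the CSQ-3, measures satisfaction, which Aim 5 compares between arms. The lower bound assumes that the full 25% attrition occurs before each assessment. The conclusion also assumes that the walk test is conducted by staff, which section V does not say outright. Consent pages are not in the documents; they might say more about what participants are told, but they could not hide the device from its wearer.

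**What to change.** 1. In section 3.1 and section V, Phase III, state blinding by role. Participants (as to the device), therapists and adherence raters are not blinded. Participants receive a neutral description of two physical activity groups. Claim masking to the hypothesis only if the recruitment post in section III is brought into line with that description; otherwise describe it as partial.
2. Name by role who conducts the post-test walk test and the 3-month calls. Where existing staff allow, use people who do not lead groups, set up Fitbits, handle Fitbit accounts or rate recordings. Ask participants not to mention their group or device, and have the tester or caller record yes or no whether the arm became known. If no such staff exist, report these roles as unblinded.
3. State whether the analysts in section III are masked. If they are, keep the Fitbit-use summary described in section IX apart from the between-arm analysis file.

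The cost is a set of text edits plus one yes/no entry per walk test and per call: 60 + 60 = 120 to 80 + 80 = 160 entries. No assessment is added and no extra staff are required. The downside is a weaker but accurate blinding claim and less freedom in assigning staff.
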